EMIQ has been shown to be effective in reducing body fat in Japanese people who have different dietary habits and lifestyle from that of a person in the United States. Thus, this study is designed to investigate if EMIQ is also effective in reducing body fat in subjects with a western lifestyle.

Quercetin, according to Seo et al [11] in addition to being a very strong antioxidant, prevents adipogenesis by regulating two sets of enzymes, a) by upregulating adipose triglyceride lipase (ATGL) and hormone sensitive lipase (HSL) expression and, b) by downregulating fatty acid synthesis (FAS), lipoprotein lipase (LPL) and adipocyte fatty acid-binding protein (aP2) expression, through expression of transcription factors such as C/EBP α , PPAR γ , SREBP-1. These observations suggest that quercetin has therapeutic potential for body fat reduction through regulating the expression of transcriptional factors and enzymes associated with adipogenesis. Dong et al [12] also reported that dietary quercetin reduces high fat diet-induced body weight gain, fat deposition, and insulin resistance and suppresses glucose uptake by adipose tissue. They reported that these effects of dietary quercetin is mediated through quercetin activating of AMPK/ACC signaling pathway which promotes fatty acid β -oxidation and suppresses fatty acid esterification into triglyceride in adipocyte. Administration of 275 mg/d for 12 weeks reduced total body fat, visceral fat and subcutaneous fat in Japanese subjects. EMIQ is classified by the Food and Drug Administration (FDA) as Generally Recognized As Safe (**GRAS**). Thus, it should be considered a safe compound in order to investigate its potential biological activities in humans.

III. Research Plan

A. Experimental Design

This is a randomized, double-blind, placebo controlled study.

B. Sample Size and Statistical Analyses

50 subjects will be required to complete this 12 week study (though 150 will be screened and 64 will be enrolled to ensure completion of 50 subjects). Subjects will be randomized 1:1 into either the treatment (EMIQ) or placebo group. The study physician, [name], will hold the code to the randomization which will be revealed upon completion of the study or if adverse event occurs.

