Screening: Volunteers that were pre-screened by telephone will be scheduled and asked to come to the MRU at the HNRCA. Volunteers will be asked to arrive fasted for 12 hours. When they arrive, volunteers will be given a Screening Consent Form along with an explanation of all procedures that will be completed at screening. Volunteers will have an opportunity to read the consent form and have any of their questions answered to their satisfaction. Once their consent is given we will begin by measuring volunteer’s vital signs, height, body weight wearing a pre-weighted pair of scrubs, and BMI. Blood samples will be collected for blood chemistry analysis. Women of childbearing potential will be subjected to a blood pregnancy test. The Beck Depression Inventory will be administered to assess for depression. Additionally, study inclusion and exclusion criteria and health history will be reviewed. Breakfast and a \$25 screening stipend will be provided once screening procedures are complete. All subjects will be mailed a copy of screening labs within 1-2 weeks following the screening visit. Volunteer’s enrollment eligibility will be determined based on meeting inclusion and exclusion criteria. Subjects with abnormal hematologic parameters, as defined by the HNRCA Nutrition Evaluation Laboratory (NEL) reference ranges, which are determined by the study physician to interfere with study outcomes, will be excluded from study participation. At the discretion of the study physician, subjects will be alerted to abnormal results that warrant follow-up with their primary care physician. Subjects with abnormal hematologic values outside the NEL reference range that do not affect study outcomes will be included at the discretion of the study physician. Note that data generated from blood draws at this visit will be used as baseline values in lieu of drawing additional blood at visit 2 for subjects that continue the study after screening.

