Visit 2, Baseline: A 10mL (2 teaspoons) blood sample will be drawn into red marble top tubes for liver and kidney function tests, insulin and adiponectin. An additional 7mL (1.4 teaspoons) of blood will be drawn into lavender top tubes for analysis of lipids. A spot urine sample will be provided for urinalysis.

Visit 3, Week 4: A 5mL (1 teaspoon) blood sample will be drawn into a gold topped tube for liver/kidney function testing.

Visit 4, Week 8: A 5mL (1 teaspoon) blood sample will be drawn into a gold topped tube for liver/kidney function testing.

Visit 5, Final: A 3mL (0.6 teaspoons) blood sample will be drawn into a lavender topped tube for CBC differential analysis. A 10mL (2 teaspoons) blood sample will be drawn into red marble top tubes for liver and kidney function tests, insulin and adiponectin. An additional 7mL (1.4 teaspoons) of blood will be drawn into lavender top tubes for analysis of lipids. A spot urine sample will be provided for urinalysis.

*Note: Visits 3 and 4 will be used to monitor participant's liver and kidney function during the study. If the study physician determines that liver function appears to be in jeopardy, subjects will be asked to discontinue the supplement and to take medical action at the discretion of the study physician.

*Note: Abnormal lab values found at screening will be provided to the volunteers in writing. Abnormal values for safety labs (those falling outside of the study physician's predetermined range) will be repeated. The study physician will be notified and determine any follow-up action.

Nutritional Intake and Physical Activity:

Subjects will receive a Food Amount Booklet and information about the 24-hour recalls at visit 1. The Dietary Assessment Unit will collect three (3) 24-hour recalls by phone (two weekdays and a weekend) between visits 1 and 2. Three recalls will be collected by phone again between visits 3 and 4 (around week 6, midway through the 12 week supplementation period) and between visits 4 and 5 (around weeks 11-12). Dietary intake data will be analyzed using Nutrition Data System for Research software version 2015, developed by the Nutrition Coordinating Center (NCC), University of Minnesota, Minneapolis, MN.

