Study participants will be contacted by a member of the study team each week either by phone or by email to monitor adherence to the intervention and to monitor self-reported health changes. Study team members will fill out a weekly log to ensure that volunteers have been contacted. If any abnormalities are reported, the study physician will be informed. The study physician will advise the participant to follow up with their primary care physician and also decide if the participant can continue with the intervention.

Participants will receive a compliance calendar used to track their supplement intake at visit 2.

Participants will be required to return any unused supplements and compliance calendar at visits 3, 4 and 5. Participants that miss a visit beyond the allowed interval (4 weeks \pm 1 week from previous visit) will be instructed to discontinue their supplement, if they have not done so already, and they will be removed from the study.

V. Location

This study will be performed at the Metabolic Research Unit and Vascular Biology Laboratory at the Jean Mayer USDA Human Nutrition Research Center on Aging at Tufts University, located at [name].

DXA scans will be performed at the Body Composition Analysis Center at Tufts University Friedman School of Nutrition and Science Policy, located at [name].

VI. Transportation

Volunteers will be required to provide their own transportation to the HNRCA. The building is accessible by public transportation. However, if

participants should choose to drive, they can obtain parking validation at a reduced cost.

VII. Personnel who will conduct the study

a. Present During Study Procedures:

Study Nurse
Study Coordinators
Principal Investigator

b. Primary Responsibility for the Following Activities

i. Obtaining Informed Consent

Authorized MRU staff
Principal Investigator
Study Coordinators

ii. Providing On-Going Information to the Study Sponsor and the IRB

Principal Investigator
Co-Investigator
Study Physician

iii. Maintaining Participant's Research Records

Authorized MRU staff
Principal Investigator
Study Coordinators

VIII. Subject Payment

Screening Stipend: \$25

Visit 1 Stipend: \$50

Visit 2 Stipend: \$150

Visit 3 Stipend: \$50

Visit 4 Stipend: \$50

Visit 5 Stipend: \$305

Subjects will only be paid for each completed visit, and will not be paid if they withdraw or are withdrawn from the study.

IX. Confidentiality

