All stipends will be mailed to participants in the form of checks 2-3 weeks after they complete each visit. Participants who are removed from the study or choose to drop out will be paid for their completed visits only, and will not be paid if they are removed or choose to drop out before the completion of any study visit. In the event of a government shutdown or any other emergency situation, stipend will be delayed until the shutdown or emergency has ended.

F. Specific Procedures Used Throughout this Study

Distribution and Storage of Dietary Supplement

Supplements and placebo will be labeled in a binary (e.g., A or B) fashion without study staff's knowledge of which is which. Both supplement and placebo will be stored in locked cabinets at the MRU. The two will be distributed to participants, in accordance with their randomization scheme, starting at visit 2. Participants will receive an extra week's worth of supplements at each visit wherein supplement is distributed in anticipation of events that may keep volunteers from attending their next visit after 4 weeks.

Weight and Height:

Body weight will be measured during each visit to the HNRCA, aside from visit 1. Participants will be asked to change into scrubs provided by MRU during weight measurement to ensure the most accurate measurement.

Height will be measured at each visit to the HNRCA except enrollment. Shoes and head dressings or ornaments will be removed. Measurements will be taken according to standard procedure.

Waist and Hip Circumference:

Waist and hip circumference will be measured at visits 2 and 5. Measurements will be taken against the skin. Waist circumference will be measured at the approximate midpoint between the lower margin of the last palpable rib and the top of the iliac crest. Hip circumference will be measured around the widest portion of the buttocks with the tape parallel to the floor. These measures will be performed in duplicate and averaged.

Resting Metabolic Rate (RMR):

RMR measures will be performed only at the visits 2 and 5. Subjects will arrive at the HNRCA in a fasted state. Subjects will undergo bed rest for 30 min prior to measurement. Systolic and diastolic blood pressure will be measured. Measures of VO_2 and VCO_2 will be made

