6. May jeopardize the subject's health and may require medical or surgical intervention to prevent one of the other outcomes listed above.

AEs are Unanticipated Problems only when they meet all three criteria in the definition of an unanticipated problem.

In the event of an Unanticipated Problem, or adverse event, staff will immediately notify the PI and study physician. Once notified, the PI, [name], will take immediate action to eliminate or minimize risk to enrolled subjects. The study physician, [name], will assess the severity of the unanticipated problem, and determine its relation to the study protocol. Each unanticipated problem will be reported, with all supporting documentation, according to the following IRB guidelines within 5 business days:

Information that does not fall under any of the categories does not require reporting to the IRB.

1. Harm experienced by a subject or other individual, which in the opinion of the investigator is **unexpected** and **related/possibly related** to the research procedures.
 - A. A harm is "**unexpected**" when its specificity and/or severity is **inconsistent** with risk information previously reviewed and approved by the IRB in terms of nature, severity, frequency, and characteristics of the study population.
 - B. A harm "**possibly related**" when there is a reasonable likelihood that the incident, experience, or outcome may have been caused by the procedures involved in the research.
- b. Information that indicates a new or increased risk, or a new safety issue. For example:
 - A. New information (e.g., an interim analysis, safety monitoring report, publication in the literature, sponsor report, or investigator finding) indicates an increase in the frequency or magnitude of a previously known risk, or

uncovers a new risk or greater risk of harm (including physical, psychological, economic, or social harm) than was previously known or recognized.

- B. An investigator brochure, package insert, or device labeling is revised to indicate an increase in the frequency or magnitude of a previously known risk, or describe a new risk
- C. Withdrawal, restriction, or modification of a marketed approval of a drug, device, or biologic used in a research protocol
- D. Complaint of a subject that indicates subjects or others might be at increased risk of harm or at risk of a new harm

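### The study physician holds the randomization code, to be opened on any adverse event, and also judges entry, relatedness and stopping, so blinding of those judgements is not ensured

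*Protocol*

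**What the plan says.** Protocol III.A: "This is a randomized, double-blind, placebo controlled study". Section III.B adds: "Subjects will be randomized 1:1 into either the treatment (EMIQ) or placebo group". The same section says that the study physician "will hold the code to the randomization which will be revealed upon completion of the study or if adverse event occurs". It does not say to whom the code is revealed, for how many subjects, or who may ask for it.

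The study physician is also given these decisions:

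- **Entry.** Section III.C leaves exclusion for major illness, and the reading of screening laboratory values, to this person. In III.E.I (Screening), subjects whose out-of-range blood values do not affect study outcomes "will be included at the discretion of the study physician".
- **Stopping on liver function** (III.E.IV, note on visits 3 and 4). "If the study physician determines that liver function appears to be in jeopardy, subjects will be asked to discontinue the supplement".
- **Continuation** (III.E.IV, Compliance). When the weekly contact brings up an abnormality, the physician will "also decide if the participant can continue with the intervention".
- **Withdrawal on health grounds** (III.C, Withdrawal/Termination Criteria). This is the physician's determination.
- **Relatedness** (III.G). The physician "will assess the severity of the unanticipated problem, and determine its relation to the study protocol".

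On masking, III.F (Distribution and Storage of Dietary Supplement) says: "Supplements and placebo will be labeled in a binary (e.g., A or B) fashion without study staff's knowledge of which is which". Neither document says that the physician's copy is sealed, that a second person controls it, or that judgements are recorded before it is opened. Section III.G states that there is no DSMB. The SAP analyses completers only.

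**The concern.** Relatedness, stopping and discretionary entry rest on judgement. A person who knows the arm can rate the same event differently, or stop one participant sooner than another, without meaning to. The relatedness scale in III.G shows this: its grades are about the intervention, and a rater who knows that a subject took placebo can hardly choose the upper ones.

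Two features make custody of the code matter here. First, a subject withdrawn by the physician does not complete, and so leaves the SAP's analysis of both the body-fat outcomes and the week-12 safety values. Second, safety is Specific Aim 2, and no independent board looks at the data a second time.

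**Working it through.** The plan gives no figure on this point to reproduce. The check compares the text across sections, with one illustrative calculation.

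**Step 1. Custody set beside decisions**

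| Function | Who, and where |
|---|---|
| Holds the code | Study physician (III.B) |
| Discretionary entry | Study physician (III.C, III.E.I); shared with a nurse for laboratory eligibility (III.E.III) and for hypertension (III.C) |
| Stopping, continuation, health withdrawal | Study physician (III.E.IV, III.C) |
| Relation of unanticipated problems | Study physician (III.G) |
| Relation of other reported adverse events | No assessor named (III.F, Volunteer Consent and Safety) |
| Analysis of DXA scans | Body composition laboratory (III.F) |

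One role has custody and most of the judgements. The DXA analysis lies outside it.

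**Step 2. Two readings of the code-holding sentence**

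- *Open list.* The physician can look up the arm at any time. Every decision by that role is then exposed, and entry decisions as well if the list shows upcoming assignments.
- *Sealed list.* The physician has it but does not look until a trigger occurs. Judgements before the first opening are then blinded.

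The text does not settle which applies, so the milder reading is taken forward.

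**Step 3. How easily the trigger is met on the sealed reading**

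The trigger is an adverse event without qualification. Section III.G defines adverse events broadly enough to include an abnormal laboratory result. Blood is drawn at visits 3, 4 and 5 after supplementation starts, and health changes are asked about weekly.

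The documents give no event rate. Let p be the chance that an enrolled subject has at least one triggering event, with subjects independent. Enrolment is 64 (III.B).

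P(at least one opening) = 1 − (1 − p)^64

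| Assumed p | Result |
|---|---|
| 1% | 1 − 0.99^64 = 47% |
| 2% | 1 − 0.98^64 = 73% |
| 5% | 1 − 0.95^64 = 96% |
| 10% | 1 − 0.90^64 = 99.9% |

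If the sentence is applied as written, an opening during the trial ranges from about an even chance to near certainty.

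**Step 4. What one opening discloses**

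The labels are binary, with A and B given as an example. If all subjects share two labels, learning one subject's arm reveals what that label means, and the other label follows. One opening can therefore disclose up to 64 − 1 = 63 other allocations to anyone who knows those subjects' labels. Whether the physician knows the labels is not stated. Nursing staff hand out the capsules, and III.E.IX gives the physician access to research records, but it does not say that the records carry the label.

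**Step 5. Order of events**

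The event that opens the code is the one whose relatedness, and the participant's continuation, must then be judged. Nothing requires those judgements to be recorded first. So even a code kept sealed until then can be open when the judgement is made.

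**Step 6. Where this can reach the results**

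The plan enrols 64 to have 50 complete, a margin of 64 − 50 = 14, or 14/64 = 21.9%. That margin covers non-completion for any reason. The number of physician-led withdrawals is not given, so the size of any bias cannot be calculated.

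**The case against.** The strongest reply is that custody is not knowledge. To say that a code will be revealed later implies that it is concealed until then; the trial is called double-blind, and staff are said not to know which label is which. This stands. A reader might infer that the physician's judgements are made unblinded, but no passage says that the physician consults the code.

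A reader might also infer that entry is steered by the next assignment. That would need a sequential list visible beforehand, which the documents do not describe. Screening decisions come before supplement is dispensed at visit 2, so the question there is allocation concealment rather than blinded assessment, and some of those decisions are shared with a nurse. This limb is conditional only.

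Nor is every causality call affected. Section III.G names the physician for unanticipated problems, while for other reported adverse events no assessor is named. Hypothesis 2 rests on measures of heart, liver and kidney function and psychological state, and the SAP plans no analysis of relatedness ratings. Withdrawal for low intake or missed visits follows stated rules. DXA scans are analysed by a separate laboratory. All of these points stand and narrow the concern.

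They do not remove it. The reply rests on the code staying closed, and the protocol itself opens it on any adverse event, with no limit to the subject concerned and no rule that judgements come first.

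**Conclusion.** The point holds as a failure to ensure blinding, not as a finding that blinding was absent. One role holds the code and makes the stopping, continuation, health-withdrawal and discretionary-entry decisions, as well as the relatedness decision for unanticipated problems. The unrestricted trigger can open the code before those judgements are made.

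Three things are exposed: relatedness calls on unanticipated problems; physician-led withdrawals, which decide who is in the completer analysis; and, only if the list is visible, concealment at entry. The reading of DXA is not exposed.

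Severity is moderate. The opening probabilities of 47% to 99.9% rest on assumed event rates of 1% to 10%, on independence between subjects, and on the trigger being applied literally. The wider disclosure rests on two shared labels that are known to the person who sees the code. No bias in the treatment comparison is quantified, because the documents give no basis for it.

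**What to change.** 1. **Custody (III.B).** Name a code holder with no role in eligibility, event assessment or withdrawal, for example a statistician or pharmacist not otherwise involved. The only pharmacy reference in the protocol is a policy on destroying returned supplement, so the role has to be assigned explicitly.
2. **Labels (III.F).** Replace the two shared labels with subject-level codes. Without this, sealed single-subject envelopes would not help, since one opening would still explain the label.
3. **Code break (III.B).** Replace the blanket adverse-event trigger with a logged, single-subject procedure that records who asked, why, when, and who was told. The clinical grounds for a break are for the sponsor and study physician to define.
4. **Order (III.C, III.E.IV, III.G).** State that severity, relatedness and continuation are recorded before disclosure where the situation allows. Name the assessor of relatedness for reported adverse events.

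The cost is protocol wording, transfer of one list and some relabelling, with one extra step in an emergency code break.

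The SAP is written in the past tense, so enrolment may be over. In that case, document who held and opened the code, when, and which entry, relatedness and stopping decisions came afterwards, and report withdrawals by arm with reasons.
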